The Dyadic Adjustment Score is a validated instrument for evaluation of adjustment in relationships between either married or unmarried cohabiting couples. It may be used at baseline to obtain a comprehensive description of the relationship and as an objective measure of change in the interaction between partners after an intervention. The DAS consists of a 32-item self-administered questionnaire that is not gender specific. It has four subscales: relationship satisfaction, cohesion, consensus, and affectional expression. The DAS takes 5-10 minutes to complete.

All women presenting with a chief complaint of 3 months of UUI or mixed urinary incontinence (MUI) with urge predominance to the Division of Female Pelvic Medicine & Reconstructive Surgery at Loyola University Medical Center who meet inclusion criteria will be approached for study participation. Women will receive a thorough explanation of the study, including the risks, benefits, and potential side effects of the study drug, and their questions will be answered. Women of childbearing age will be counseled that they should be using an effective method of birth control during the study. They will sign an informed consent document. They will also be given a 3 day voiding diary to be completed at home. Prior to completing the 3 day voiding diary, patients currently taking an anticholinergic medication will undergo a 2 week wash out period during which

they will not take any drug. They will also be given a letter describing the study to give to their partner.

Women with a diagnosis of UUI or MUI, urge predominant, who have consented to participate and whose partners consent to participate will return to the clinic with completed study questionnaires (PISQ-12, PFIQ-7, MESA, GRISS, and DAS).

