Subjects will be recruited from all racial and ethnic groups. Race and ethnicity will be determined by self-reporting according to the guidelines of The Office of Management and Budget Directive No. 15. On the screening questionnaire, subjects will be allowed to choose from 2 ethnic categories, "Hispanic or Latina" and "Not Hispanic or Latina". They will also choose from 5 racial categories: American Indian or Alaska Native; Asian; Black or African American; Native Hawaiian or Other Pacific Islander; and White. Appropriate definitions will be included on the questionnaire.

Women will eligible for *inclusion* in the study if they are:

- Age \geq 18 years, and
- In a relationship with a male partner for at least 3 months, and
- Not pregnant (pregnancy test will be done at study enrollment) or planning to become pregnant, and

- Have a diagnosis of UUI or MUI, urge predominant, based on recall
- Are interested in medical management of their symptoms and are candidates for Vesicare, and
- Able to provide informed consent and complete the written questionnaires.

Women will **excluded** from participation in the study if they have:

- PVR > 200 ml at initial visit
- Significant outflow obstruction
- Persistent/recurrent UTI
- Bladder stones
- A diagnosis of chronic interstitial cystitis
- Undergone pelvic irradiation
- Current pelvic malignancy
- Narrow angle glaucoma
- Urinary or gastric retention
- Current use of a tricyclic antidepressant
- A neurologic diagnosis that could affect bladder function (MS)
- A diagnosis of chronic pelvic pain
- An active psychotic disorder

Women will also be **ineligible** for participation if they:

- Or their partner is non-English speaking
- Decline permission for the study team to approach their partner regarding participation

Statistical Analysis

Power Analysis

While the change in the overall GRISS score is the primary outcome in this study, the sample size for this study is based upon published research utilizing the DAS (i.e., which also measures relationship satisfaction).

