A prior study of the relative effectiveness of two behavioral interventions in the treatment of marital discord randomized 45 couples to a known intervention, an experimental intervention, or a wait list (control group)(16). This sample size was adequate to demonstrate a significant change in DAS score in response to the study intervention. Similarly, a study of 36 couples detected significant changes in DAS scores following an intervention that consisted of several variants of marital therapy (17). Similar sample sizes have been used in the published literature of studies using the DAS as an indicator of improvement in marital quality (18, 19). This study will recruit 100 couples (200 subjects) with the assumption of a 50% response rate to the study drug (Vesicare). This will allow for a final sample size of 40-50 couples, consistent with that of other studies in the published literature.

Statistical Analysis Plan

In this study, the Global Impression of Improvement (GII) score is used to indicate response to therapy following three months of treatment, where response to treatment comprises those who rate their Global Impression of Improvement (GII) as "a little better", "much better", or "very much better". Conversely, non-response to treatment comprises those who rate their GII as "no change", "a little worse", "much worse", or "very much worse".

Participants' baseline characteristics will be stratified by sex and compared between responders and non-responders using Pearson chi-square tests. For females, this includes comparisons between responders and non-responders on age (i.e., ≥ 60 versus < 60), race, marital status, education attainment, years living with a partner (i.e., ≥ 30 versus < 30), body mass index (i.e., ≥ 30 versus < 30 kg/m²), menstrual cycle, vaginal parity, prior treatment for pelvic floor disorders, prior surgery, and prior treatment for overactive bladder treatment. For males, this includes comparisons between responders and non-responders on age (as specified above), current sexual activity, general health, and medical history of hypertension, erectile dysfunction, arthritis, diabetes, cancer, heart disease, and depression. For these baseline comparisons, expected frequencies will be monitored and Fisher's exact tests will be used when such values are sparse.

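### Women already on an anticholinergic at enrolment are pooled with untreated women in an unadjusted Aim 2 comparison, which could dilute or confound the responder contrast

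*Combined protocol and SAP*

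**What the plan says.** - **Entry of treated women (Methodology).** The plan states that "patients currently taking an anticholinergic medication will undergo a 2 week wash out period during which" they are off drug. No agent is named or excepted. The washout is placed "Prior to completing the 3 day voiding diary".
- **Baseline questionnaires (Methodology).** Consenting women "will return to the clinic with completed study questionnaires (PISQ-12, PFIQ-7, MESA, GRISS, and DAS"). The text does not say whether these forms are filled in before, during or after the washout.
- **Eligibility (Subjects and Recruitment).** One inclusion criterion reads "Are interested in medical management of their symptoms and are candidates for Vesicare, and"; candidacy is not defined. The only exclusion based on a drug in use is "Current use of a tricyclic antidepressant". Current or past use of an anticholinergic, or of Vesicare, is not mentioned.
- **Grouping (Statistical Analysis Plan).** Responders are "those who rate their Global Impression of Improvement (GII) as" at least slightly improved after three months. The state against which the woman judges improvement is not given.
- **Treatment history (Statistical Analysis Plan).** The baseline characteristics compared between responders and non-responders include "prior treatment for pelvic floor disorders, prior surgery, and prior treatment for overactive bladder treatment".
- **Aim 2 tests (Statistical Analysis Plan).** Women's GRISS change is compared by an independent-samples t-test, with a rank-sum test as a check. Male partners' change is compared between the same two groups. Neither comparison has a covariate, a stratum or a sensitivity analysis by treatment history.

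**The concern.** Aim 2 is meant to measure what successful treatment does for the relationship. Two kinds of women enter it: those on no anticholinergic at enrolment, and those who stop one for two weeks and then take Vesicare. For the second kind, better at three months may be judged against the washout and so describe a return to an earlier treated state. If she judges against her pre-study state, the same course may be rated as no change. The grouping variable can therefore mean different things for the two kinds of women.

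Two consequences are possible. If couples in the second group show little or no difference in GRISS change between responders and non-responders, pooling shrinks the contrast (dilution). If treatment history also affects GRISS change by a route other than response, and its frequency differs between the response groups, the contrast is partly a contrast of treatment histories (confounding). The groups are self-rated and not randomised, so nothing in the design balances them. The baseline comparison may show an imbalance, but the plan does not say what would then be done. As worded, it also does not separate women on drug at enrolment from past users.

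**Working it through.** **The plan's own figure.** Power Analysis gives 100 couples, a 50% response rate and a final 40-50 couples. 100 x 0.50 = 50 reproduces the upper end. The lower end needs a further 20% loss that is not stated: 50 x 0.80 = 40. No alpha, power, effect size or SD is given, so there is no power statement to reproduce. What follows is illustration.

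**Assumed inputs (none is in the documents).** Difference between responders and non-responders of 0.60 SD among women on no anticholinergic; share of current users p = 10% to 30%; two-sided 5% t-test. Group sizes are 50 v 50 (100 couples, 50% response, no losses) or 40 v 40 (20% lost).

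**Dilution.** With users spread evenly over both groups and a fraction f of the contrast present among them:

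pooled difference = 0.60 x [(1 - p) + p x f]

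| p | f | Pooled difference (SD) | Power 50 v 50 | Power 40 v 40 |
|---|---|---|---|---|
| 0 | - | 0.60 | 84% | 76% |
| 10% | 0 | 0.60 x 0.90 = 0.54 | 76% | 67% |
| 20% | 0 | 0.60 x 0.80 = 0.48 | 66% | 56% |
| 30% | 0 | 0.60 x 0.70 = 0.42 | 55% | 46% |
| 10% | 0.5 | 0.60 x 0.95 = 0.57 | 81% | 71% |
| 30% | 0.5 | 0.60 x 0.85 = 0.51 | 71% | 62% |

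The rows with f = 0 are the worst case short of a reversed contrast. With f = 1 there is no dilution.

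**Confounding.** Suppose response has no effect on GRISS change and current users improve 0.5 SD less than the others (assumed):

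bias = (share of users in responders - share in non-responders) x (-0.5 SD)

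The standard error with 50 v 50 is sqrt(2/50) = 0.20 SD.

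- 30% v 30%: bias 0; false-positive rate 5%.
- 20% v 40%: (-0.20) x (-0.5) = +0.10 SD; 7.9%.
- 10% v 50%: (-0.40) x (-0.5) = +0.20 SD; 17%.
- 40% v 20%: (+0.20) x (-0.5) = -0.10 SD; 7.9%, in the opposite direction.

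The bias can be nil or of either sign.

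**What each remedy can do.** Adding treatment status as a covariate removes the bias in the second illustration. It does not undo the first: with users spread evenly, the adjusted difference is still the average of the two subgroup contrasts, (1 - p) x 0.60 + p x f x 0.60. Only an analysis without the current users recovers 0.60 SD. Its size is (1 - p) x 50 per group: 45 v 45 at p = 10% (power 80%) and 35 v 35 at p = 30% (power 70%). From 40 v 40 it is 36 v 36 to 28 v 28 (71%-60%).

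**The case against.** The strongest reply is that none of this is shown to happen.

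- A reader might infer that women already taking Vesicare will be enrolled. The documents do not say so. It follows only from the absence of an exclusion, and the undefined candidacy criterion could be applied to keep them out. Women must also present with urge incontinence as their chief complaint, so one doing well on her drug is not the obvious recruit.
- A reader might infer that couples with a treated woman receive no new treatment. That is not supported. A woman who switches from another agent receives a new drug. Methodology offers a dose increase after 4 weeks. If baseline GRISS is completed off drug, follow-up on drug is a real change in treatment.
- Harder-to-treat women falling among the non-responders is not in itself confounding. That requires an effect of treatment history on GRISS change apart from response, and the documents give no evidence of one.
- The power losses rest on assumed inputs, and the largest on an extreme one.
- Aim 2 concerns successful treatment, not first treatment, so admitting both kinds of women is compatible with it.

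Most of this stands, and it limits the point to a possibility of unknown size. It does not remove the point. The washout is tied to the voiding diary and not to GRISS, so an off-drug baseline is not assured. Pooling affects users of any anticholinergic, whether or not Vesicare users enter. A descriptive comparison of earlier treatment leaves the Aim 2 estimates unadjusted.

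**Conclusion.** The point holds as a limited one. Women on an anticholinergic at enrolment can enter after a washout, are pooled with untreated women, and are not distinguished in either Aim 2 comparison. The contrast could be diluted or confounded. The documents give neither the share of such women nor their distribution over the response groups, so size and direction cannot be determined. Both depend partly on when baseline GRISS is completed relative to the washout.

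The illustrated loss of power with 50 v 50, from 84% to 76%-55%, assumes a 0.60 SD difference, 10% to 30% current users spread evenly, and no contrast among them. With half the contrast among them it is 81%-71%, about the power of the restricted analysis itself (80%-70%). For that reason the figures do not support a reading that the main Aim 2 conclusion should move to the untreated subset. This is a cheap improvement to the SAP and not a flaw that invalidates Aim 2.

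**What to change.** 1. Carry anticholinergic use at enrolment (yes/no, with the agent if recorded) into the SAP as a baseline variable.
2. Report both Aim 2 comparisons, women and male partners, adjusted for it. This addresses confounding by treatment at entry.
3. Pre-specify a sensitivity analysis of both comparisons in couples where the woman took no anticholinergic at enrolment. This addresses dilution, which adjustment does not.
4. Keep the full-sample analysis as the main one, and qualify the Aim 2 conclusion if the restricted result differs.
5. State whether baseline GRISS was completed before, during or after the washout, since the interpretation depends on it.

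**Cost.** Some SAP wording and one variable. Its yes/no form must already be known to apply the washout. The agent is not an explicitly listed data item and may not be available for every woman. The restricted analysis has fewer couples (45 v 45 to 35 v 35 from 50 v 50, on the assumed shares) and should be read as supportive. Eligibility, washout and dosing are unchanged.

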They will be given Vesicare 5mg with instructions for use. After 4 weeks of use, we anticipate that 50% of patients will note improvement. Those who do not feel that their symptoms are adequately controlled will have the option of increasing to 10 mg per day for the remaining 8 weeks of the study. After 12 weeks of medication use, patients will have a follow up visit, they will be asked to again complete all of the PISQ-12, PFIQ-7, MESA, GRISS, and DAS as well as the Overall Quality of Life Related to Urinary Incontinence Questionnaire. Male partners will also complete a second set of questionnaires either in the clinic or at home after their partner has undergone 12 weeks of treatment. Patients will be given a total of 16 weeks of Vesicare to allow for some variation in scheduling follow up and to ensure that they are currently taking Vesicare at the time that they complete their follow up questionnaires.

Subjects and Recruitment

Loyola's clinical research team is well-suited to successfully recruit women to this study. Our division has four clinical faculty members, all of whom are NIH funded investigators who participate in large clinical and surgical trials through the Urinary Incontinence Treatment Network and the Pelvic Floor Disorders Network. In addition, we have 4 full-time research nurses and a data entry manager. The entire group is fully supportive of this research.

Recruitment of men for studies on female urinary incontinence is a new area of research. This study would be the first to exam relationship dynamics from the perspective of the male partner using validated methods. Based upon a small pilot study of male partners that was conducted at our center, we believe that the recruitment of male partners is a feasible goal. Because there is no direct benefit to the male partner and given the personal nature of the data collected, compensation of the male partners (travel and parking) is reasonable and likely to give a more representative sample.

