For Aim 1, baseline Golombok Rust Inventory of Sexual Satisfaction (GRISS) scores will be compared between matched male and female partners using a paired samples *t*-test. The difference between female and male responses will be assessed for normality using a QQ plot and for outliers using a boxplot. If parametric assumptions are violated, conclusions may be confirmed using a Wilcoxon signed-rank test.

For Aim 2 we will subtract participants' overall 3-month GRISS score from their overall baseline score and compare this change in GRISS between those who respond and do not respond to solifenacin using an independent samples *t*-test. As before, the normal distribution of the change score in each response group will be assessed graphically using a QQ plot and for outliers using a box-plot. If parametric assumptions are violated, conclusions may be confirmed using a non-parametric Wilcoxon rank-sum test.

Finally, healthy male partners of female participants also complete the GRISS at baseline and after their female partner completes approximately 12-16 weeks of solifenacin treatment for UUI symptoms. For these male partners, a change score will be calculated by subtracting their baseline score from the follow-up score. This change score will be compared between male partners of female participants who respond to solifenacin versus male partners of female participants who do not respond to solifenacin.

All statistical analysis will be conducted using SAS Version 9.4 (SAS Institutes, Cary, NC) with the input of a Biostatistician.

References

1. Shaw C. A systematic review of the literature on the prevalence of sexual impairment in women with urinary incontinence and the prevalence of urinary leakage during sexual activity. *Eur Urol*. 2002 Nov;42(5):432-40.
2. Hilton P. Urinary incontinence during sexual intercourse: A common, but rarely volunteered, symptom. *Br J Obstet Gynaecol*. 1988 Apr;95(4):377-81.

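### Follow-up and response status are tied to about 12 weeks of drug use, so couples in which the woman stops early may fall outside both Aim 2 groups

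*Combined protocol and SAP*

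**What the plan says.** **Timing for the woman.** The Methodology describes one post-baseline assessment: "After 12 weeks of medication use, patients will have a follow up visit". The questionnaires are repeated at that visit. The drug supply runs to 16 weeks, to absorb scheduling variation and "to ensure that they are currently taking Vesicare at the time that they complete their follow up questionnaires".

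**Timing for the partner.** The Methodology places his second set of questionnaires "after their partner has undergone 12 weeks of treatment". The SAP places it "after their female partner completes approximately 12-16 weeks of solifenacin treatment for UUI symptoms".

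**Classification.** In the SAP, "the Global Impression of Improvement (GII) score is used to indicate response to therapy following three months of treatment". Any rating of improvement counts as response, and "non-response to treatment comprises those who rate their GII as" unchanged or worse. There is no category for a woman without a rating. The GII is not named among the follow-up instruments in the Methodology.

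**Use.** For Aim 2 the SAP will "compare this change in GRISS between those who respond and do not respond to solifenacin using an independent samples" *t*-test. Male partners are compared according to the woman's response status. The Power Analysis names change in overall GRISS as the primary outcome.

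**Not stated.** The documents do not say whether a woman who stops the drug is still assessed, or how she is classified. They give no dropout rate, missing-data method or sensitivity analysis.

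**The concern.** The study has no randomised control, so non-responders are the only comparison group for Aim 2. Each timing statement presupposes about 12 weeks or three months of treatment. A woman who stops at week 5, for example, never reaches the event that triggers her own visit or her partner's. Without a GII rating she is neither a responder nor a non-responder, and her partner has no group either.

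Entry to the analysis would then depend on staying on the drug. That is a post-baseline event plausibly related to both benefit and tolerability. If women who stop differ in GRISS change from those who stay in the same response group, the contrasts for women and for men are distorted. Questionnaires not collected around week 12 cannot be recovered at analysis.

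**Working it through.** **Inputs from the plan (Power Analysis):** 100 couples recruited, 50% response assumed, "final sample size of 40-50 couples".

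**The plan's own figure.** 100 × 0.50 = 50, the top of the stated range. The bottom, 40, would need 100 × 0.50 × 0.80, a 20% loss that the plan does not state. Both ends count expected responders. If a loss is read into the range, it is therefore 10 of 50 responders, and it says nothing about how many non-responders would be lost.

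**Assumptions for the illustration (none is in the plan):** 10 or 20 women stop and go unrated; stoppers differ from retained women of the same response status by 0 to 0.5 SD in mean GRISS change; two-sided 5% test, 80% power. The starting point is 50 responders and 50 non-responders.

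**Step 1. Observed response rate** = retained responders / all retained.

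| Stoppers | All would be non-responders | Half and half | All would be responders |
|---|---|---|---|
| 10 | 50/90 = 55.6% | 45/90 = 50% | 40/90 = 44.4% |
| 20 | 50/80 = 62.5% | 40/80 = 50% | 30/80 = 37.5% |

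**Step 2. Precision.** Detectable difference = (1.960 + 0.842) × √(1/n₁ + 1/n₂), normal approximation.

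- 50 v 50: 2.802 × 0.2000 = 0.560 SD
- 50 v 40: 2.802 × 0.2121 = 0.594 SD
- 50 v 30: 2.802 × 0.2309 = 0.647 SD

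Power for a true difference of 0.56 SD falls from 80% to 75% and then to 68%.

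**Step 3. Shift in the contrast.** Score change so that larger means more improvement. Let d be the stoppers' mean change minus that of retained women of the same response status. Then

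retained contrast − full contrast = (non-responders lost / 50) × d(non-responders) − (responders lost / 50) × d(responders).

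- 10 non-responders lost, d = ±0.5 SD: 10/50 × 0.5 = 0.10 SD either way.
- 20 non-responders lost, d = ±0.5 SD: 20/50 × 0.5 = 0.20 SD either way. The contrast is understated if stoppers did worse than retained non-responders and overstated if they did better.
- d = 0: no shift.
- 10 lost from each group: the terms can cancel or add, up to 0.10 + 0.10 = 0.20 SD, although the observed response rate stays at 50%. An unchanged response rate is therefore no evidence that selection is harmless.

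The same formula applies to the men, using their own GRISS changes.

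**The case against.** The strongest reply is that the plan never excludes anyone. The sentence about being on drug at follow-up explains how much drug is dispensed. The 12-week and three-month phrases can be read as timing for the intended course, and a woman who stopped could still attend and give a GII rating. A reader might infer a stated rule that bars stoppers from assessment. The documents do not support that, and this part of the reply stands.

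A reader might also infer that stoppers come from the non-response group, so that the response rate is overstated. That does not follow either. The mildest improvement rating already counts as response, so a woman with some benefit who stops for side effects would be a lost responder. The response rate is also a planning assumption, not an aim or outcome.

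On the remedy, three cautions are fair:

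- A GII taken whatever the drug status could credit solifenacin with improvement due to a later therapy.
- Counting every unrated stopper as a non-responder would misclassify some women.
- Imputing GRISS without response status in the model would pull the contrast toward zero.

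These cautions shape the fix but do not remove the need for it. On the milder reading, the plan still leaves open whether stoppers are assessed and how they are classified, and the primary contrast depends on both.

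**Conclusion.** The point holds as a gap in the plan. Followed as written, the plan triggers no assessment for a couple in which the woman stops early and gives that couple no place in Aim 2. The Aim 2 contrasts may therefore be limited to couples who stayed on drug.

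Selection bias is possible but not established. It needs stoppers who differ in GRISS change from retained women (or partners) of the same response status, and the documents give neither the number of stoppers nor their outcomes. The ranges in the working show what could happen if 10 or 20 of 100 women stop; they do not estimate what will happen. The stated range of 40 to 50 couples cannot be used as evidence of a planned 20% dropout.

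This is a cheap improvement worth making, not a demonstrated flaw in the result.

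**What to change.** **Methodology, and the SAP paragraph on male partners.** Schedule the GII, GRISS and DAS for the woman, and the GRISS and DAS for her partner, at 12 weeks after the start of study drug, whether or not she is still taking it. Name the GII among the follow-up instruments. Record drug status, the reason for any stop, and any other UUI treatment.

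**SAP, definition of response.** Keep the GII at that time as the classifier and report how many women are unrated, with reasons. Add three sensitivity analyses for the Aim 2 contrasts:

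1. women still on drug only, with their partners;
2. unrated women who stopped counted as non-responders;
3. multiple imputation of missing GRISS, with baseline GRISS and response status in the model. Where the GII is also missing, response status must be imputed as well.

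**Cost.** A few sentences in two sections, the existing questionnaires sent to couples in which the woman stopped, and three additional analyses. The reported response rate may turn out less favourable. No treatment rule changes.

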Specific Aim #1: To define the levels of relationship satisfaction and sexual function among couples with the female partner having primarily: UUI symptoms and mixed urinary incontinence (urge predominant).

Hypothesis 1: Couples with (female partner) UUI will have lower levels of relationship satisfaction and sexual function based upon validated measures of sexual function and relationship cohesion.

Specific Aim #2: To measure the impact of successful treatment of UUI on the relationship.

Hypothesis 1: Successful treatment with Vesicare will result in improvement in relationship satisfaction and sexual function for both male and female partners.

We expect that the results of this prospective study will allow us to objectively quantify the degree to which intimate relationships are affected by UUI thus filling a critical gap in our knowledge. We also expect to demonstrate that successful treatment of UUI leads to an improvement in relationship satisfaction and sexual function.

Significance of the Proposed Work

Chronic illness places emotional, physical, and financial burdens upon both the patient and her partner, and can be a significant source of stress in a relationship. The symptoms of UUI inherently pose greater social challenges than those faced by women with other forms of pelvic floor disorders. For example, women with UUI may avoid social situations due to fear of having an accident or may be reluctant to participate in activities during which it may be difficult to find a bathroom. The resulting social isolation impacts both members of the dyad and may serve as a source of relationship discord. Changes in sexual function and perceived intimacy, including non-intercourse intimacy, as well as communication may be new sources of stress in a previously healthy relationship or may serve to amplify pre-existing relationship problems.

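### Must the rating that defines treatment response be tied to a named form and a printed question before the Aim 2 comparisons can be relied on?

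*Combined protocol and SAP*

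**What the plan says.** Under the heading Statistical Analysis Plan, response is set by one self-rating: "the Global Impression of Improvement (GII) score is used to indicate response to therapy following three months of treatment". The rule continues, "where response to treatment comprises those who rate their Global Impression of Improvement (GII) as", followed by three grades of improvement. Non-response is then defined by four categories: no change and three grades of worsening.

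The resulting groups are used three times. Baseline characteristics of women and of men are compared between them. For Aim 2, the plan will "compare this change in GRISS between those who respond and do not respond to solifenacin". For the men, "This change score will be compared between male partners of female participants who respond to solifenacin", against the partners of women who do not respond. The Power Analysis section names change in overall GRISS as the primary outcome.

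The Methodology section lists what the woman completes after 12 weeks: "PISQ-12, PFIQ-7, MESA, GRISS, and DAS as well as the Overall Quality of Life Related to Urinary Incontinence Questionnaire". The GII is not in that list. It is also absent from the baseline questionnaires, the items taken from medical records, the male partners' questionnaires, and the references given for the instruments (references 11 to 15).

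**The concern.** The GII decides who counts as a responder, so it decides which couples stand on each side of the primary comparison. A reader who tries to trace it back finds its name only in the analysis section. The one 12-week form that is neither described nor referenced, the quality-of-life questionnaire related to incontinence, may hold the item, but no sentence says so.

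The question itself is also missing. Specific Aim #2 is "To measure the impact of successful treatment of UUI on the relationship", which calls for a rating of the bladder condition. The answer categories would fit that, but they would also fit a question about how the woman feels in general. A general rating could overlap with sexual and relationship satisfaction, so grouping and outcome would be partly the same thing and the difference in GRISS change would be hard to interpret. If the rating were not collected at all, there would be no groups to compare.

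**Working it through.** No figure in the plan is in dispute, so the check sets the texts side by side.

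**1. Where the rating is named.** Only in the Statistical Analysis Plan. The forms at the woman's 12-week visit are PISQ-12, PFIQ-7, MESA, GRISS, DAS and the quality-of-life questionnaire, six in all. Five carry references in the Methodology section, so 6 − 5 = 1 is undescribed. The omission is confirmed.

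**2. What is needed to code the groups.**

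| Element | Given? | Where |
|---|---|---|
| Answer categories | Yes: 3 + 4 = 7 | Statistical Analysis Plan |
| Cut for response | Yes: 3 response, 4 non-response | Statistical Analysis Plan |
| Time point | Yes: three months of treatment | Statistical Analysis Plan |
| Whose rating | Yes: men are grouped by the woman's response | Statistical Analysis Plan, last comparison |
| Host form | No | – |
| Question text | No | – |

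The four elements that determine group membership are all present. The two that are missing identify the paper source. They do not alter how an answer is coded.

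**3. Which visit.** The Methodology section describes one post-treatment questionnaire visit, after 12 weeks, and the woman completes the GRISS there. The analysis section uses her 3-month GRISS and a three-month GII. The four-week point, at which the dose may be raised, has no questionnaires attached. The rating and the follow-up GRISS therefore belong to the same visit on any ordinary reading.

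**4. Whether there is an open four-week window.** One could take 16 − 12 = 4 weeks from two statements: "Patients will be given a total of 16 weeks of Vesicare to allow for some variation in scheduling follow up", and the male partners completing the GRISS "after their female partner completes approximately 12-16 weeks of solifenacin treatment for UUI symptoms". The first is a drug-supply allowance and the second times the men's questionnaire. Neither states a window for the woman's rating.

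**5. What is being rated.** The SAP calls the GII an indicator of response to therapy, labels the groups by response to solifenacin, and describes solifenacin as treatment for UUI symptoms. Specific Aim #2 uses the same idea. No sentence points to a rating of general well-being.

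**6. Whether missing question text is peculiar to this item.** It is not. GRISS and DAS are described by length and subscales. PISQ-12 and PFIQ-7 share a line of description. MESA has a name, a reference and an eligibility cut on its urge index. No item is printed for any of them. The GII is the one whose full set of answer categories is written out.

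**The case for a change.** The best case for a change is that this variable carries more weight than its documentation suggests. GRISS is named, referenced, described and scheduled; the GII, which divides the sample for the GRISS comparison, has none of that outside the SAP. It has no literature reference, so its question cannot be looked up as the others' can. The Methodology section also offers other notions of improvement (improvement noted at four weeks, symptoms adequately controlled, follow-up MESA, quality of life related to incontinence), so a reader could wonder which is meant. Two or three sentences would settle it.

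Part of this stands. The visit list and the analysis section do not match, and naming the form would be tidy. The rest does not carry. The other notions of improvement do not compete, because the SAP states which rating defines response and where the cut falls. Overlap between grouping and outcome depends on the question being about general well-being, and nothing in the text supports that. Absence from a list does not show that the rating would go uncollected, since the categories are specified in enough detail to suggest an existing item. The added sentences would record what staff and analysts would take from the form in hand; they would change no group, test or estimate.

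**Conclusion.** No change to the plan is called for. What remains is a clerical mismatch: one item used in the analysis is not named among six forms at one visit. Its size cannot be put as an effect on results, because the documents show none; group assignment is fully determined by the stated categories, cut, time point and respondent.

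This conclusion rests on two readings. The first is that the rating was meant to be taken at the single follow-up visit, which the matching three-month timing supports. The second is that it concerns the treated bladder condition, which the SAP's own description of response supports. If either proved false when checked against the form in use, the question would be one of validity and would need to be looked at again. Nothing in the documents gives reason to expect that.
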